7.5.4 End-of-Treatment Visit

An End-of-Treatment visit must be conducted for all subjects who discontinue from treatment. This visit must occur within 2 weeks or 4 weeks after the last dose of investigational product of Induction Therapy or OLE/LTE Therapy, respectively.

If the subject discontinues during Induction Therapy, the assessments listed in Table 9.1 for End-of-Treatment/Week 12 should be performed at the End-of-Treatment visit. A sigmoidoscopy will be performed at End-of-Treatment/Week 12 if the subject discontinues more than 8 weeks after Baseline visit; the sigmoidoscopy may be performed up to 4 weeks after the last dose of study medication. Post-treatment follow-up visits should subsequently occur 4, 8 and 14 weeks after the End-of-Treatment/Week 12 visit.

If the subject discontinues during OLE/LTE therapy, the assessments listed in Table 9.2 for End-of-Treatment/Week 52 should be performed at the End-of-Treatment visit. A sigmoidoscopy will be performed at End-of-Treatment/Week 52 if the subject discontinues more than 8 weeks after the Week 12 visit; the sigmoidoscopy may be performed up to 8 weeks after the last dose of study medication. Post-treatment follow-up visits should subsequently occur 4, 8 and 12 weeks after the End-of-Treatment/Week 52 visit.

The Investigator must complete all applicable End-of-Treatment visit procedures (e.g., sigmoidoscopy, safety laboratory parameters, ECG, physical examination, vital signs) and applicable eCRF pages for subjects who discontinue treatment and include the reason for discontinuation of treatment.

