10.1.2 Safety

The safety and tolerability of KHK4083 will be determined by physical examination, vital signs, body weight, 12-lead ECGs, and clinical laboratory findings; and the number and percentage of subjects reporting AEs (frequency, severity, and relationship to investigational product), SAEs, and treatment discontinuation due to AEs.

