5.1 Subject enrollment and disposition

The number of Subjects screened and in each visit week will be presented by treatment Cohort. Subject disposition will be summarized including the number and percentage of subjects enrolled and completed each of the study periods (Double-Blind Induction Therapy Period, Double-Blind Induction Therapy Follow-up Period, OLE/LTE Therapy Period, and OLE/LTE Therapy Follow-up Period), discontinued from the treatment, discontinued the study and completed the study. The number of subjects who moved from LTE to OLE Therapy Period. The definitions for completions and discontinuations are shown below;

- Subjects who have the CRF page of “Week 12” will be defined as those who completed Induction Therapy.
- Subjects who have the CRF page of “Follow-up 3 - Subjects not enrolling in LTE Therapy Period” or “Follow-up 3 - Subjects not enrolling in OLE Therapy Period” will be defined as those who completed Double-Blind Induction Therapy Follow-up Period.
- Subjects who have the CRF page of “Week 52” will be defined as those who completed OLE/LTE Therapy Period.
- Subjects who have the CRF page of “Follow-Up 3 - Post Long Term Extension Therapy” will be defined as those who completed OLE/LTE Therapy Follow-up Period.
- Subjects who have the CRF page of “End of treatment” will be defined as those who discontinued the treatment.
- Subjects who have “No” for the question of “Did the subject complete the study?” on the CRF page of “End of study” will be defined as those who discontinued the study.
- Subjects who have “Yes” for the question of “Did the subject complete the study?” on the CRF page of “End of study” will be defined as those who completed the study.

The number of subjects in the Safety Analysis Set and FAS will be provided. Disposition information will be provided overall and separately for each treatment Cohort.

	Forms			
	Title	Statistical Analysis Plan Template		
	Code	Version	Effective Date	Page
	FRM_ST03_032	01	23 Apr 2015	25 of 53

The reasons why subjects were excluded from any analysis set will be listed individually. In addition table summaries of the primary reason for discontinuation/withdrawal from the study will be presented by means of number and percentage of subjects by treatment cohort, period and overall.

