8.1 Adverse events

The onset date of an adverse event will be compared to the date of investigational product dosing to determine if the adverse event is treatment-emergent or not. Adverse events with an onset date on or after the first date of investigational product dosing will be classified as treatment emergent adverse events (TEAEs). If the adverse event onset date is missing or partial, the date will be compared as far as possible with the date of investigational product dosing. Adverse events will be assumed to be TEAEs unless there is clear evidence (through comparison of partial dates) to suggest that the adverse event started prior to receiving the dose of investigational product.

TEAE will be summarized in a table that presents the number and percentage of subjects with any TEAE, with any serious TEAE, with any drug-related TEAE, with any TEAE leading to discontinuation and death overall and within each treatment period (Double-Blind Induction Therapy Period, LTE Therapy Period, and OLE Therapy Period) by treatments (each KHK4083 dose level versus placebo). It will also include the total number of adverse events in each of these categories. All TEAEs will be summarized showing the number and percentage of subjects for each event with a start time within the treatment period (i.e., Double-Blind Induction Therapy Period, LTE Therapy Period, and OLE Therapy Period) and by treatments (each KHK4083 dose level versus placebo) during Induction Therapy or KHK4083 dose level versus placebo during OLE /LTE Therapy Period. All TEAEs will be summarized by SOC and Preferred Term as well as by Preferred Term in decreasing frequency. Two additional summary tables are presented for serious TEAEs and Related TEAEs.

	Forms			
	Title	Statistical Analysis Plan Template		
	Code	Version	Effective Date	Page
	FRM_ST03_032	01	23 Apr 2015	35 of 53

Listings of all adverse events (including non-treatment-emergent events) will be provided. This listing will be presented by dose cohort and will include site-subject identifier, adverse event (SOC, Preferred Term, reported term), start date, stop date, study day, severity grade, seriousness, relationship to drug, action taken with study treatment, and outcome. Also SAEs will be listed in a similar format as described above. Deaths which are adverse events leading to death, adverse events leading to discontinuation and adverse events with withdrawal of investigational product also will be listed in the same manner.

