Table 14.3.1-2.4	Treatment-Emergent Adverse Events By System Organ Class, Preferred Term and Relationship to Investigational Product During Double-Blind Therapy Period and Double-Blind Therapy Follow-Up Period / Safety Analysis Set
Table 14.3.1-2.5	Treatment-Emergent Adverse Events By System Organ Class, Preferred Term and Relationship to Investigational Product During Double-Blind Induction Therapy Period / Safety Analysis Set
Table 14.3.1-2.6	Treatment-Emergent Adverse Events By System Organ Class, Preferred Term and Relationship to Investigational Product During Open-Label Extension Therapy Period and Open-Label Extension Therapy Follow-Up Period / Safety Analysis Set
Table 14.3.1-3.1	Treatment-Emergent Adverse Events By Maximum Severity, System Organ Class and Preferred Term During Double-Blind Therapy Period and Double-Blind Therapy Follow-Up Period / Safety Analysis Set
Table 14.3.1-3.2	Treatment-Emergent Adverse Events By Maximum Severity, System Organ Class and Preferred Term During Double-Blind Induction Therapy Period / Safety Analysis Set
Table 14.3.1-3.3	Treatment-Emergent Adverse Events By Maximum Severity, System Organ Class and Preferred Term During Open-Label Extension Therapy Period and Open-Label Extension Therapy Follow-Up Period / Safety Analysis Set
Table 14.3.1-4.1	Serious Treatment-Emergent Adverse Events By System Organ Class and Preferred Term During Double-Blind Therapy

Forms

Title Statistical Analysis Plan Template

Code	Version	Effective Date	Page
FRM_ST03_032	01	23 Apr 2015	45 of 53

Number	Title
	Period and Double-Blind Therapy Follow-Up Period / Safety Analysis Set
Table 14.3.1-4.2	Serious Treatment-Emergent Adverse Events By System Organ Class and Preferred Term During Double-Blind Induction Therapy Period / Safety Analysis Set
Table 14.3.1-4.3	Serious Treatment-Emergent Adverse Events By System Organ Class and Preferred Term During Open-Label Extension Therapy Period and Open-Label Extension Therapy Follow-Up Period / Safety Analysis Set
Table 14.3.1-5.1	Treatment-Emergent Adverse Events Leading to Discontinuation from The Study By System Organ Class and Preferred Term During Double-Blind Therapy Period and Double-Blind Therapy Follow-Up Period / Safety Analysis Set
Table 14.3.1-5.2	Treatment-Emergent Adverse Events Leading to Discontinuation from The Study By System Organ Class and Preferred Term During Double-Blind Induction Therapy Period / Safety Analysis Set

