Table 14.3.1-5.3	Treatment-Emergent Adverse Events Leading to Discontinuation from The Study By System Organ Class and Preferred Term During Open-Label Extension Therapy Period and Open-Label Extension Therapy Follow-Up Period / Safety Analysis Set
Table 14.3.4-1.1	Vital Signs and Body Weight and Change from Baseline During Double-Blind Therapy Period and Double-Blind Therapy Follow-Up Period / Safety Analysis Set
Table 14.3.4-1.2	Vital Signs and Body Weight and Change from Baseline During Open-Label Extension Therapy Period and Open-Label Extension Therapy Follow-Up Period / Safety Analysis Set
Table 14.3.4-2.1	Summary of Clinical Laboratory Values-Hematology During Double-Blind Therapy Period and Double-Blind Therapy Follow-Up Period / Safety Analysis Set
Table 14.3.4-2.2	Summary of Clinical Laboratory Values-Hematology During Open-Label Extension Therapy Period and Open-Label Extension Therapy Follow-Up Period / Safety Analysis Set
Table 14.3.4-2.3	Summary of Clinical Laboratory Values- Serum Chemistry During Double-Blind Therapy Period and Double-Blind Therapy Follow-Up Period / Safety Analysis Set
Table 14.3.4-2.4	Summary of Clinical Laboratory Values- Serum Chemistry During Open-Label Extension Therapy Period and Open-Label Extension Therapy Follow-Up Period / Safety Analysis Set
Table 14.3.4-2.5	Summary of Clinical Laboratory Values- Coagulation Profile During Double-Blind Therapy Period and Double-Blind Therapy Follow-Up Period / Safety Analysis Set
Table 14.3.4-2.6	Summary of Clinical Laboratory Values- Coagulation Profile During Open-Label Extension Therapy Period and Open-Label Extension Therapy Follow-Up Period / Safety Analysis Set

Forms

Title Statistical Analysis Plan Template

Code	Version	Effective Date	Page
FRM_ST03_032	01	23 Apr 2015	46 of 53

Number	Title
Table 14.3.4-2.7	Summary of Clinical Laboratory Values- Urinalyses During Double-Blind Therapy Period and Double-Blind Therapy Follow-Up Period / Safety Analysis Set
Table 14.3.4-2.8	Summary of Clinical Laboratory Values- Urinalyses During Open-Label Extension Therapy Period and Open-Label Extension Therapy Follow-Up Period / Safety Analysis Set
Table 14.3.4-2.9	Shift Table of Clinical Laboratory Values -Hematology During Double-Blind Therapy Period and Double-Blind Therapy Follow-Up Period / Safety Analysis Set

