9.6 Listings

Number	Title
Listing 16.2.1-1.1	Disposition of Subjects - / All Subjects
Listing 16.2.1-1.2	Screening Failures / Screening Failure Subjects
Listing 16.2.2-1	Protocol Deviations / Randomized Subjects
Listing 16.2.2-2	Violations of Inclusion / Exclusion Criteria / Randomized Subjects
Listing 16.2.3-1	Populations for Analysis / Randomized Subjects
Listing 16.2.4-1	Demographics and Baseline Characteristic / Randomized Subjects
Listing 16.2.4-2	Baseline UC Assessment and UC Diagnosis / Randomized Subjects
Listing 16.2.4-3	Pregnancy Test / Randomized Subjects
Listing 16.2.4-4	Medical / Surgical History / Randomized Subjects
Listing 16.2.4-5	Physical Examinations / Randomized Subjects
Listing 16.2.5-1	Prior and Concomitant Medications / Randomized Subjects
Listing 16.2.5-2	Study Medication Administration / Randomized Subjects
Listing 16.2.5-3	Study Medication Duration and Number of Dose / Randomized Subjects
Listing 16.2.6-1	MMES at All Study Visits / Randomized Subjects
Listing 16.2.6-2.1	UCEIS and Baron Endoscopic Score at All Study Visits / Randomized Subjects
Listing 16.2.6-2.2	Total and Partial Mayo Clinic Scores at All Study Visits / Randomized Subjects
Listing 16.2.6-2.3	Clinical Response at Week 12 and Week 52 / Randomized Subjects
Listing 16.2.6-3.1	Total and 4 Subscale IBDQ Scores at All Study Visits / Randomized Subjects
Listing 16.2.6-3.2	Corticosteroid Dosages and The Duration of Glucocorticoid-Free Treatment / Randomized Subjects
Listing 16.2.7-1	Pre-Treatment Adverse Events / Summary of All Subjects / Randomized Subjects
Listing 16.2.7-2.1	Treatment-Emergent Adverse Events / Randomized Subjects
Listing 16.2.7-2.2	Serious Treatment-Emergent Adverse Events / Randomized Subjects
Listing 16.2.7-2.3	Treatment-Emergent Adverse Events Leading to Deaths / Randomized Subjects
Listing 16.2.7-2.4	Treatment-Emergent Adverse Events Leading to Discontinuation / Randomized Subjects
Listing 16.2.7-2.5	Treatment-Emergent Adverse Events with Withdrawal of Investigational Product / Randomized Subjects

Forms

Title Statistical Analysis Plan Template

Code

Version

Effective Date

Page

FRM_ST03_032

01

23 Apr 2015

52 of 53

Number	Title
Listing 16.2.8-1	Vital Signs / Randomized Subjects
Listing 16.2.8-2	Clinical Laboratory Values-Hematology / Randomized Subjects
Listing 16.2.8-3	Clinical Laboratory Values-Clinical Chemistry / Randomized Subjects
Listing 16.2.8-4	Clinical Laboratory Values- Coagulation Profile / Randomized Subjects

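### No planned table is clearly specified to report treatment discontinuation due to AEs: the by-term tables are titled for leaving the study, and the overall summary row does not say which event it counts

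*SAP*

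**What the plan says.** **Endpoint.** Protocol 10.1.2, under the primary endpoints, and SAP 3.5 both include, as a number and percentage of subjects, "SAEs, and treatment discontinuation due to AEs".

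**Two separate events.** SAP 5.1 works from CRF items. Subjects with an End of treatment page "will be defined as those who discontinued the treatment". Subjects with a No to the question on study completion, on the End of study page, "will be defined as those who discontinued the study". Protocol 7.5.4 keeps subjects who stop drug during induction under observation: "Post-treatment follow-up visits should subsequently occur 4, 8 and 14 weeks after the End-of-Treatment/Week 12 visit". Leaving the study is handled separately in Protocol 7.5.5.

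**Planned tables.** SAP 9.4 has three by-term discontinuation tables:
- 14.3.1-5.1: double-blind therapy with its follow-up, with the same from-the-study wording.
- 14.3.1-5.2: "Treatment-Emergent Adverse Events Leading to Discontinuation from The Study By System Organ Class and Preferred Term During Double-Blind Induction Therapy Period".
- 14.3.1-5.3: "Treatment-Emergent Adverse Events Leading to Discontinuation from The Study By System Organ Class and Preferred Term During Open-Label Extension Therapy Period", together with its follow-up.

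The overall TEAE summaries (Tables 14.3.1-1.1 to 1.4) follow SAP 8.1, which counts subjects "with any drug-related TEAE, with any TEAE leading to discontinuation and death overall and within each treatment period". In disposition, SAP 5.1 counts subjects who stopped treatment but tabulates primary reasons only for leaving the study.

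**Listings.** SAP 8.1 and 9.6 plan one listing of TEAEs leading to discontinuation (16.2.7-2.4) and another, 16.2.7-2.5: "Treatment-Emergent Adverse Events with Withdrawal of Investigational Product / Randomized Subjects".

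**The concern.** The endpoint is about staying on drug; the titles of the by-term tables are about staying in the study. A subject whose drug is stopped for an AE and who then attends all follow-up visits meets the endpoint but may not meet the condition in the table titles. The gap widens as sites get better at keeping such subjects in follow-up, which is what Protocol 7.5.3 asks of them. Safety and tolerability is the Part A primary objective and the dose groups are small, so one or two subjects counted differently would visibly change the reported percentages.

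**Working it through.** The plan gives no figure on this point to reproduce. The check is whether the endpoint can be traced to a table, followed by the size of one misclassified subject.

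**Step 1: can the two events separate?** Yes. Take a subject who stops drug for an AE during induction. An End of treatment page makes that subject a treatment discontinuation under SAP 5.1. Protocol 7.5.4 then schedules three more visits. If those are attended and the study-completion question is answered Yes, SAP 5.1 makes the same subject a study completer.

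**Step 2: where would that subject appear?**

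| Planned output | Event as specified | Subject shown? |
|---|---|---|
| Tables 14.3.1-5.1 to 5.3 | TEAE leading to leaving the study | No, as titled |
| Overall TEAE row (14.3.1-1.1 to 1.4, and the Week 12 version) | TEAE leading to discontinuation, not said from what | Cannot be determined |
| Disposition reasons (SAP 5.1) | Reason for leaving the study | No |
| Disposition count (SAP 5.1, Table 14.1-1) | Stopped treatment, any reason | Yes, without the AE reason |
| General TEAE tables (14.3.1-2.x, and by severity in 3.x) | Any TEAE | Yes, not marked as leading to a stop |
| Listing 16.2.7-2.5 | TEAE with drug withdrawn | Yes, individually |

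No row is clearly a count and percentage, by treatment, of subjects who stopped drug because of an AE.

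**Step 3: which meaning does the overall row carry?** SAP 8.1 lists AEs leading to discontinuation and AEs with drug withdrawn as two items. That suggests the first means leaving the study, but this is inference; the SAP does not define it.

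**Step 4: size per subject.** One subject left out of a group of n lowers that group's percentage by 100/n points. Group sizes come from Protocol 8.1.4.1 and SAP 3.2.
- One Part A dose, n = 9: 100/9 = 11.1 points.
- Recommended dose, Parts A and B combined, n = 9 + 18 = 27: 100/27 = 3.7 points.
- Placebo, n = 3 × 3 + 6 = 15: 100/15 = 6.7 points.

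The documents give no rate of stopping for AEs and no rate of completing follow-up afterwards. The number of subjects affected is therefore unknown and could be zero.

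**The case against.** The case on the other side is substantial.

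- The endpoint asks only for a number and percentage, not a breakdown by term. The overall row in SAP 8.1 gives such a figure by treatment and period, is not restricted to leaving the study, and its induction version is in the Week 12 list (SAP 9.4.1). It may be the intended endpoint row. This stands as a possibility, and it is why the row needs a definition.
- A reader might infer that these subjects vanish from the report, or that a poorly tolerated dose would look well tolerated. The documents do not support that. The event is still a TEAE in the by-term tables, the treatment stop is counted in disposition, exposure tables show shorter treatment, and Listing 16.2.7-2.5 names the event. What is not clearly tabulated is the AE as the reason for stopping.
- A reader might also infer that the Part B dose choice is affected. It is not tied to these tables: Protocol 6.3 and 8.1.4.1 rest continuation and escalation on the Safety Monitoring Committee's review of cumulative safety data.
- The titles may be loose wording. Protocol 7.5.3 speaks of removal from the study when discussing a drug stop, and 7.5.5 asks for the reason treatment was discontinued at a visit about leaving the study. The table shells are a separate document (SAP 9.7), and the documents do not say how study completion is recorded for a subject who is off drug. This makes the effect conditional. It does not remove the mismatch, because SAP 5.1 defines the two events separately and the titles are the only specification of these three tables in the documents.

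**Conclusion.** The point holds as a mismatch between a named endpoint and its tables. Followed as titled, Tables 14.3.1-5.1 to 5.3 report TEAEs leading to study discontinuation, not treatment discontinuation. The only other candidate table row is undefined, and drug withdrawal for an AE is clearly identified only in listings. AE-related treatment discontinuation can therefore be understated in the three by-term tables, by the points per subject shown above.

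This rests on two assumptions: that the programmed filter follows the table titles, and that a subject who stops drug and finishes follow-up is recorded as completing the study. If either fails, the counts may be right and only the labels need correcting. The documents do not support saying that the tolerability result is biased, only that these tables can understate it. The change is worth making before the tables are programmed.

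**What to change.** 1. In SAP 8.1, state that the discontinuation row of the overall TEAE summaries (Tables 14.3.1-1.1 to 1.4, and the Week 12 version in 9.4.1) counts subjects with a TEAE for which the action taken with study treatment was drug withdrawn.
2. Use the same rule for Tables 14.3.1-5.1 to 5.3 and retitle them *Leading to Discontinuation of Investigational Product*.
3. If study discontinuation due to AE is also of interest, show it as a separate, labelled row.
4. Adding Table 14.3.1-5.2 to the Week 12 list is optional.

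The cost is SAP wording, three titles and one selection rule. No new data are needed: Protocol 10.6.7 has the action taken on investigational product recorded for each AE, and SAP 8.1 already lists it. The CRF is not among the documents, so confirm that its response categories separate permanent withdrawal from temporary interruption.

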9.4.1 Tables for Un-Blinded 12 Week Induction Therapy Data

Number	Title
Table 14.1.1	Disposition of Subjects for Induction Therapy Period
Table 14.1.4.1	Demographics (Safety Analysis Set)
Table 14.2.1.1	Baseline and Change from Baseline of Modified Mayo Endoscopic Score (MMES) at Week 12 (induction Therapy)
Table 14.2.1.2	Analysis of Change from Baseline in MMES at Week 12
Table 14.2.2.1	Baseline and Change from Baseline in UCEIS at Week 12
Table 14.2.2.2	Baseline and Change from Baseline in Total Mayo Clinic Score at Week 12
Table 14.2.2.3	Partial Mayo Clinic Score during Induction Therapy
Table 14.2.2.4	Clinical Improvement (%) at Week 12 in MMES, Modified Baron Endoscopic Score, Mucosal Healing, Clinical Response and Clinical Remission
Table 14.2.2.5.1	Analysis of Change from Baseline in UCEIS at Week 12
Table 14.2.2.5.2	Analysis of Change from Baseline in Total Mayo Clinic Score at Week 12
Table 14.2.2.5.3	Analysis of Change from Baseline in Partial Mayo Clinic Score at Week 12

Forms

Title Statistical Analysis Plan Template

Code

Version

Effective Date

Page

FRM_ST03_032

01

23 Apr 2015

48 of 53

Number	Title
Table 14.2.3.9.1	Baseline and Change from Baseline in Mayo Clinic Score - Stool Frequency during 12 Week Induction Therapy
Table 14.2.3.9.3	Baseline and Change from Baseline in Mayo Clinic Score - Rectal Bleeding during 12 Week Induction Therapy
Table 14.2.3.9.7	Baseline and Change from Baseline in Modified Baron Endoscopic Score at 12 Week Induction Therapy
Table 14.2.3.9.9	Baseline and Change from Baseline in UCEIS Subscore - Vascular Pattern at 12 Week Induction Therapy
Table 14.2.3.9.11	Baseline and Change from Baseline in UCEIS Subscore - Bleeding at 12 Week Induction Therapy
Table 14.2.3.9.13	Baseline and Change from Baseline in UCEIS Subscore - Erosions and Ulcers at 12 Week Induction Therapy
Table 14.3.1.1.3	Overall Summary of Treatment Emergent Adverse Events during Induction Therapy
Table 14.3.1-2.2	Treatment-Emergent Adverse Events by System Organ Class and Preferred Term during Double-Blind Induction Therapy Period
Table 14.3.1.2.5	Treatment-Related Treatment-Emergent Adverse Events by System Organ Class, Preferred Term during Double Blind Induction Therapy.
Table 14.3.1.4.2	Serious Treatment-Emergent Adverse Events by System Organ Class and Preferred Term during Double-Blind Induction Therapy Period

